#### 3.2. Secondary Endpoints and Clinical Outcomes

- Mitral regurgitation reduction at 30 days, 6 months, 1 year and annually thereafter over baseline
- All-cause mortality at 30 days, 6 months, 1 year, and annually thereafter
- Recurrent heart failure hospitalization at 30 days, 6 months, 1 year, and annually thereafter
- Re-intervention rates for mitral regurgitation at 30 days, 6 months, 1 year and annually thereafter
- Composite of major adverse events (MAE) defined as cardiovascular mortality, stroke, myocardial infarction, new need for renal replacement therapy, severe bleeding and re-intervention for study device related complications at 6 months, 1 year and annually thereafter
- Change in Left Ventricular End Diastolic Volume (LVEDV) at 6 months and 1 year and annually thereafter over baseline

- Change in Left Ventricular End Systolic Volume (LVESV) at 6 months and 1 year and annually thereafter over baseline
- Change in Pulmonary Artery Systolic Pressure at 6 months and 1 year and annually thereafter over baseline
- Change in 6MWT distance at 6 months and 1 year over baseline
- Change in Quality of Life (QoL) score, as measured by Kansas City Cardiomyopathy Questionnaire (KCCQ), and EQ5D at 30 days, 6 months and 1 year and annually thereafter over baseline
- Change in NYHA Functional Classification at 6 months and 1 year and annually thereafter over baseline
- Change in BNP/NT-pro-BNP level at 6 months and 1 year and annually thereafter over baseline
- Change in tricuspid regurgitation at 6 months and 1 year and annually thereafter over baseline
- Change in effective regurgitant orifice area (EROA) at 30 days, 6 months, 1 year and annually thereafter over baseline
- Change in mitral regurgitant volume at 30 days, 6 months and 1 year and yearly thereafter over baseline

#### 4. ANALYSIS POPULATIONS

- **Intent-to-treat population**

The intention-to-treat (ITT) population includes all patients in whom the study procedure has been attempted (i.e., incision). The ITT population does not include roll-in patients.

- **Per-protocol population**

The per-protocol (PP) population includes all patients in the ITT population in whom the study device was introduced in the body, and do not have any major protocol deviations.

- **Implanted population**

The implanted population includes all patients in whom the study device was implanted in the body at the time of the patient's exit from the cardiac catheterization laboratory.

- **Roll-in population**

Up to three roll-in patients per site may be allowed, but not required (e.g., for sites with sufficient prior experience with the system). The study Sponsor will review each situation to determine when a site may start enrolling in the ITT population.

The PP population will be the primary analysis population for performance and safety assessment. The ITT population will be used for additional safety analysis. Additional analyses of performance and safety data using the implanted population will be performed if it is clinically meaningful in addition to the PP analysis. Subgroup analysis by etiology may be performed. For patients with mixed etiology, the echo core lab will determine the dominant etiology for analysis. All analyses will be performed separately for the roll-in population.

A first analysis will be performed when 30 patients complete 30-day follow-up, and a second analysis when all patients complete their 30-day follow-up.

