8.2.5 Unanticipated Adverse Device Effect

Unanticipated adverse device effect (UADE) means any serious adverse effect on health or safety or any life-threatening problem or death caused by, or associated with, a device, if that effect, problem, or death was not previously identified in nature, severity, or degree of incidence in the investigational plan or application (including a supplementary plan or application), or any other unanticipated serious problem associated with a device that relates to the rights, safety, or welfare of subjects. (21 CFR part 812.3 (s)).

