9.2 Analysis Population

- **Intent-to-treat population**

The intention-to-treat (ITT) population includes all patients in whom the study procedure has been attempted (i.e., incision).

- **Per-protocol population**

The per-protocol (PP) population includes all patients in whom the study device was introduced in the body, and do not have any major protocol deviations.

- **Roll-in population**

Up to three roll-in patients per site may be allowed, but not required (e.g., for sites with sufficient prior experience with the system). The study Sponsor will review each situation to determine when a site may start enrolling in the ITT population.

The PP population will be the primary analysis population for performance and safety assessment. The ITT population will be used for additional safety analysis. Subgroup analysis by etiology may be performed. For patients with mixed etiology, the echo core lab will determine the dominant etiology for analysis.

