11 DEVIATIONS FROM CLINICAL INVESTIGATION PLAN

11.1 Protocol Deviation

If an Investigator or designee contacts a Clinical Affairs representative to obtain prior approval for a change to the clinical study requirements, the approval or disapproval will be documented in writing. A copy of the approval or disapproval will be forwarded to the Investigator and a copy will be maintained in the study files.

A major protocol deviation or noncompliance are those that may have a significant impact on subject safety, well-being, the subject's willingness to participate in the study, or that may compromise the integrity of the study data and analysis, including:

- a) Subject implanted/treated with study device not having met eligibility criteria at the time of implant/treatment.
- b) Informed Consent not signed or signed after the initiation of non-standard of care, research related assessments.
- c) UADE not reported to IRB/EC/Sponsor within the required timeframe
- d) Unauthorized use/implant of an investigational device

A minor protocol deviation or noncompliance is unlikely to have a significant impact on subject safety, wellbeing, or is unlikely to compromise the integrity of the study data and analysis. All protocol deviations or noncompliances will be reported to the IRB/EC, as required.

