##### Performance:

- Device success: device is deployed as intended and the delivery system is successfully retrieved as intended at the time of the patient's exit from the cardiac catheterization laboratory. Per device analysis.
- Procedural success: device success with evidence of MR reduction  $\leq$  MR2+ at discharge and without the need for a surgical or percutaneous intervention prior to hospital discharge. Per patient analysis.
- Clinical success: procedural success with evidence of MR reduction  $\leq$  MR2+ and without MAEs at 30 days. Per patient analysis.

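### The primary per-protocol set drops attempts ended before device entry and patients with a late-reported UADE, and no all-attempted success rate is planned

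*SAP*

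**What the plan says.** SAP section 4 and Protocol 9.2 give the same rule: "The PP population will be the primary analysis population for performance and safety assessment". ITT begins at incision and, in the SAP, leaves out roll-in patients. PP is the part of ITT "in whom the study device was introduced in the body, and do not have any major protocol deviations".

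Protocol 11.1 defines major deviations broadly, as those that "may have a significant impact on subject safety, well-being" or affect other listed matters such as data integrity. It then gives an open list of examples. Item (c) is "UADE not reported to IRB/EC/Sponsor within the required timeframe". Protocol 8.2.5 defines a UADE as "any serious adverse effect on health or safety or any life-threatening problem or death caused by, or associated with, a device", if not previously identified, and extends it to "any other unanticipated serious problem associated with a device that relates to the rights, safety, or welfare of subjects".

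The role of ITT is limited: "The ITT population will be used for additional safety analysis". SAP 6.3 names no population for device, procedural or clinical success, or for the Kaplan-Meier analysis of MAE, so the section 4 rule applies to all of them. The only other set that SAP 4 offers for performance is the implanted population. It is conditional, and it also omits attempts that ended without an implant.

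**The concern.** A primary set should not lose patients for reasons tied to outcome. PP can do so in two ways.

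- **Attempts that end after incision but before device entry.** These are failed procedures. The FDA Technical Success definition in SAP 6.6 requires successful access, so it treats failed access as a failure. PP takes the same patient out of the denominator. A bleed or perforation during such an attempt would also leave the primary MAE rate.
- **Patients whose UADE was reported late.** This exclusion arises after treatment. It needs a serious device-associated event or problem to have occurred, followed by an administrative lapse.

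No text says that PP membership is fixed before outcomes are known. There is no control arm to share the bias. The reported rates are the study's result, and a stated objective is to guide later study designs.

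**Working it through.** **Inputs.** Set definitions are from SAP 4 and the deviation list from Protocol 11.1. The analysis population of 60 is from SAP 2.2, and the first analysis at 30 patients from SAP 4. Exact (Clopper-Pearson) 95% intervals follow SAP 6.1b. The documents give no expected event, failure or exclusion rate, and the 60 rests on precedent studies of 30 to 35 patients (Protocol 9.1), so there is no planned rate to reproduce. All event counts below are assumptions. I take 60 attempted patients with complete 30-day follow-up, so that Kaplan-Meier equals the simple proportion.

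**Step 1: trace each type of patient.**

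| After incision | ITT | PP | Effect on primary success rates |
|---|---|---|---|
| Device never introduced | in | out | not counted |
| Device introduced, procedure fails, no major deviation | in | in | counted as failure |
| Device introduced, UADE reported late | in | out | not counted |

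**Step 2: effect of one exclusion.** With n attempted, x MAE patients and s successes:

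- MAE patient excluded: x/n − (x−1)/(n−1) = (n−x)/[n(n−1)] fall in the MAE rate
- event-free patient excluded: x/(n−1) − x/n = x/[n(n−1)] rise in the MAE rate
- failure excluded: s/(n−1) − s/n = s/[n(n−1)] rise in the success rate

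For n = 60, n(n−1) = 3540.

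- MAE patient excluded, x = 4: 56/3540 = 1.58 points. The rate goes from 4/60 = 6.7% (1.8 to 16.2) to 3/59 = 5.1% (1.1 to 14.1). For x = 1 the fall is 59/3540 = 1.67 points, and for x = 10 it is 50/3540 = 1.41.
- Event-free patient excluded, x = 4: 4/3540 = 0.11 points, to 4/59 = 6.8%. One excluded MAE patient outweighs 13 event-free exclusions: 3/(59−13) = 3/46 = 6.5%, still below 6.7%.
- Failure excluded, s = 54: 54/3540 = 1.53 points. The rate goes from 54/60 = 90.0% (79.5 to 96.2) to 54/59 = 91.5% (81.3 to 97.2). For s = 50 the rise is 1.41 points, and for s = 59 it is 1.67.

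For n = 30, n(n−1) = 870.

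- MAE: 2/30 = 6.7% to 1/29 = 3.4%, a fall of 28/870 = 3.22 points.
- Success: 27/30 = 90.0% to 27/29 = 93.1%, a rise of 27/870 = 3.10 points.

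**Step 3: several attempts ended before device entry.** Assume 3 failures within PP and k further attempts with no device introduced, scored as failures in ITT.

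| k | PP success | ITT success | Gap (points) |
|---|---|---|---|
| 1 | 56/59 = 94.9% (85.9 to 98.9) | 56/60 = 93.3% (83.8 to 98.2) | 1.6 |
| 3 | 54/57 = 94.7% (85.4 to 98.9) | 54/60 = 90.0% (79.5 to 96.2) | 4.7 |
| 6 | 51/54 = 94.4% (84.6 to 98.8) | 51/60 = 85.0% (73.4 to 92.9) | 9.4 |

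The PP rate barely moves as k grows, while the ITT rate falls by 1/60 = 1.7 points per patient.

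**Step 4: does it matter which set the 60 counts?** The documents do not say whether the 60 are ITT or PP patients. If they are PP, one excluded MAE patient gives 4/61 = 6.6% against 3/60 = 5.0%, a similar shift.

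**Step 5: would naming ITT be enough?** Not by itself. The endpoint starts "Procedural success: device success with evidence of MR reduction", and device success is analysed per device. A patient with no device introduced has no device result, and SAP 6.1b drops patients without evaluable data from the denominator. A scoring rule is needed as well.

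**The case against.** The case for leaving the plan alone has several parts.

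- **The first group may be small.** The protocol uses study device as a synonym for the whole PASCAL system, and Protocol 3.8 describes the guide sheath as part of it. If sheath entry counts as introduction, only attempts ended between incision and sheath entry are lost. That narrows the group but does not empty it.
- **The UADE route is narrow.** Most MAE components are on the anticipated list in Protocol 6.1, and a UADE need not be a health event. The other listed major deviations concern eligibility, consent and authorisation. This is correct.
- **Safety events are not hidden.** An ITT safety analysis is planned, SAP 7.7 reports adverse events for each analysis cohort, and SAP 7.1 provides a subject-level disposition listing. For MAE the issue is therefore which rate is primary. None of this supplies an all-attempted success rate.
- **The table shells are in a separate document, and the FDA success definitions name no population.** An ITT table may exist there. Nothing in the SAP text assigns one, however, and the FDA definitions are different endpoints.
- **PP as primary is prespecified in both documents, and the study has no performance goal.** A supportive ITT table would close the narrowest gap, and changing the primary set needs a protocol amendment (Protocol 14). These points limit the severity. They do not justify primary rates that can omit failures because they were failures.

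**Conclusion.** The concern holds. Followed as written, the plan removes from the primary rates procedures that failed before device entry, and patients with a serious device-associated event or problem that was reported late. The SAP text states no all-attempted analysis of procedural or clinical success.

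The size is unknown. On the assumed counts, each excluded MAE patient lowers the MAE rate by 1.4 to 1.7 points at 60 patients, and each excluded failure raises success by the same amount. At 30 patients the shift is about 3 points. The intervals overlap widely. Failures with the device introduced and no major deviation remain in PP. For attempts ended before device entry, the effect on success has one direction only, since every such patient is a failure.

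This should be fixed. It does not threaten a pass/fail decision, because there is none. It affects the reported rates and what later designs take from them.

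**What to change.** 1. Make ITT (all attempted, without roll-ins) the primary set for 30-day MAE, procedural success and clinical success. Keep PP as supportive, and leave device success per device.
2. State that an ITT patient with no device introduced counts as a failure for procedural and clinical success and stays in the denominator, notwithstanding SAP 6.1b.
3. Limit PP exclusions to deviations fixed at or before the procedure, such as Protocol 11.1(a), (b) and (d). Remove 11.1(c) as a ground for exclusion, and fix the PP list before outcome tables are run.
4. List every ITT patient outside PP with the reason and the 30-day outcome.

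The cost is new wording in SAP 4 and Protocol 9.2, with the amendment that Protocol 14 requires, and a rerun of the tables. No new data collection should be needed, because Protocol 7.8.7.11 keeps patients who receive no device until the 30-day visit. If results have already been seen, report both sets and say when the change was made. The reported rates may be slightly less favourable.

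### Per-patient success in the SAP's supplementary implanted population is biased upward, because patients without an implant fail by definition yet leave the denominator

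*SAP*

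**What the plan says.** SAP section 4 defines four populations. For the implanted one: "The implanted population includes all patients in whom the study device was implanted in the body at the time of the patient's exit" from the catheterization laboratory. Its use is described in one sentence: "Additional analyses of performance and safety data using the implanted population will be performed if it is clinically meaningful". The sentence goes on to place these analyses on top of the PP analysis. No endpoints are listed, and no criterion is given for when the condition is met. SAP section 8 declares the population as an addition to the protocol and gives its clinical relevance as the reason.

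The same part of section 4 sets the main analysis: "The PP population will be the primary analysis population for performance and safety assessment". PP consists of "all patients in the ITT population in whom the study device was introduced in the body, and do not have any major protocol deviations". Of ITT, which starts at incision and excludes roll-ins, it says: "The ITT population will be used for additional safety analysis". Roll-in patients are to be analysed separately throughout.

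Under SAP section 3.1, device success means that the "device is deployed as intended and the delivery system is successfully retrieved as intended" by the time the patient leaves the laboratory, counted per device. Procedural success is per patient and requires device success. Clinical success is per patient and requires procedural success. SAP section 6.3, which gives the methods for these endpoints, names no population, so section 4 alone decides where they may be computed.

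**The concern.** Membership of the implanted population is itself a result of the procedure. It is settled when device success is settled, and it overlaps heavily with what that endpoint measures. A success rate computed in this set is conditioned on part of the success it reports. Failure to implant is one of the things the performance endpoints exist to detect, and protocol section 6.1 lists failure to deliver the device and conversion to open surgery among the anticipated events.

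Missing data do not justify the exclusion at 30 days. Protocol section 7.8.7.11 keeps patients who undergo the procedure without receiving a device in the study until the 30-day visit, so their 30-day status can be obtained.

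At stake is a second, higher set of success rates from a single-arm study with no comparator, produced under a condition that the plan leaves undefined.

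**Working it through.** The documents give no assumed implant-failure, success or MAE rate, and the sample size rests on precedent, so there is no plan figure to reproduce. The counts below are assumptions chosen to show direction and size.

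**Inputs.** N = 60 is the analysis population (SAP section 2.2). Let k be the number of patients in whom the device was introduced but not implanted at exit (assumed, 0 to 6), and s the number of per-patient successes (assumed). For simplicity, all 60 patients are in PP, and PP and the implanted set differ only by the k patients. Intervals are exact Clopper-Pearson 95%, as in SAP section 6.1.

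**Per-patient success.** A non-implanted patient cannot be a success, so s is the same in both sets:

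- PP rate = s/N
- implanted-set rate = s/(N − k)
- difference = s·k / [N(N − k)], which is positive whenever k > 0 and s > 0

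With s = 54 and k = 3, PP gives 54/60 = 90.0% (79.5 to 96.2) and the implanted set gives 54/57 = 94.7% (85.4 to 98.9). The difference is 54 × 3 / (60 × 57) = 162/3420 = 4.7 percentage points. Holding s at 54 and varying how many of the 6 failures are non-implants:

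| k | PP | Implanted set |
|---|---|---|
| 0 | 54/60 = 90.0% | 54/60 = 90.0% |
| 1 | 90.0% | 54/59 = 91.5% |
| 2 | 90.0% | 54/58 = 93.1% |
| 3 | 90.0% | 54/57 = 94.7% |
| 4 | 90.0% | 54/56 = 96.4% |
| 5 | 90.0% | 54/55 = 98.2% |
| 6 | 90.0% | 54/54 = 100% |

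The ceiling shows the same thing. With k = 3, the highest possible procedural success is 57/60 = 95.0% (86.1 to 99.0) in PP, against 57/57 = 100% (93.7 to 100) in the implanted set. If 51 patients reach clinical success, the rates are 51/60 = 85.0% (73.4 to 92.9) and 51/57 = 89.5% (78.5 to 96.0).

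**30-day MAE.** Let e be the number of patients with an event among the implanted and f the number among the k non-implanted. With complete 30-day follow-up, the Kaplan-Meier estimate equals the simple proportion:

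- PP rate = (e + f)/N
- implanted-set rate = e/(N − k)
- the implanted-set rate is the lower one only if f/k > e/(N − k)

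With e = 3 and k = 3:

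| Events among the 3 non-implanted | PP | Implanted set |
|---|---|---|
| 0 | 3/60 = 5.0% | 3/57 = 5.3% |
| 1 | 4/60 = 6.7% | 5.3% |
| 3 | 6/60 = 10.0% | 5.3% |

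Success moves in one direction. MAE can move either way.

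**Membership.** PP is written as a subset of ITT, and ITT excludes roll-ins. The implanted definition carries neither limit. Up to 60 roll-ins are allowed beside the 60 analysis patients (SAP section 2.2).

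**The case against.** The strongest reply is that nothing primary depends on this set. The SAP says that these analyses come on top of PP, SAP section 8 discloses the population openly, and the study is descriptive, with no hypothesis test or performance goal that a higher rate could satisfy. That stands, and it limits the weight of the point.

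Five stronger readings are tempting, and the documents do not support them.

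- *Implant failures disappear from the trial's success and MAE rates.* They do not. PP needs only that the device was introduced, so a patient whose implant was attempted and abandoned stays in the primary rates unless there is a major deviation. ITT keeps every attempted non-roll-in patient for safety.
- *The implanted set necessarily shows a lower MAE rate.* The second table shows that the rate can rise slightly.
- *Device success is close to 100% by construction.* Device success is counted per device and also needs correct deployment and retrieval of the delivery system. A poorly deployed implant, a retrieval failure, or one failed device beside one implanted device all remain in the set as failures. A patient who dies with the device in place also meets the definition as worded.
- *Roll-ins will be mixed in.* Section 4 calls for separate roll-in analyses, so the intent is probably to exclude them. The definition simply does not say so.
- *No MAE should be summarised in implanted patients.* Patients without a device leave at the 30-day visit, so later MAE is observed essentially only in implanted patients. A summary of late MAE in that set is legitimate.

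The table shells, a separate document under SAP section 10, may list the endpoints. They are not available here. The shift is also modest beside the intervals, and it is zero if every patient is implanted. None of this changes the direction of the success bias that section 4 permits.

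**Conclusion.** The point holds for per-patient success in the supplementary implanted population. As written, the SAP permits procedural and clinical success rates that exclude patients who fail by definition, and those rates are biased upward whenever at least one patient is not implanted and at least one implanted patient succeeds. Under the assumed 54 successes in 60 patients, the shift is 4.7 percentage points with 3 non-implants, and the rate runs from 91.5% to 100% over 1 to 6 non-implants. The upper end requires every failure to be a non-implant. Any assumed non-implant in whom no device was introduced is already outside PP, which would narrow the gap between PP and the implanted set.

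For 30-day MAE the conclusion is conditional: the rate is understated only if non-implanted patients have events more often than implanted ones. The primary PP rates are not affected for patients who had the device introduced and have no major deviation. The missing restriction to ITT is a drafting gap. The undefined condition for running the analyses would by itself be only missing detail. It matters here because it makes a favourable figure optional. This is an inexpensive improvement to a supporting analysis and does not undermine the primary one.

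**What to change.** In SAP section 4:

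1. Define the implanted population as a subset of ITT and label it supportive.
2. List its endpoints: post-implant echo and functional outcomes (MR grade, EROA, regurgitant volume, LV volumes, NYHA class, KCCQ, 6MWT) and, if wanted, MAE after 30 days.
3. State that device, procedural and clinical success and 30-day MAE are reported in PP and ITT and not in the implanted set. At present ITT is assigned only to safety, so a patient with an incision but no device introduced enters no named performance analysis. Adding ITT closes that gap as well.
4. Replace the condition with a commitment to run the listed analyses whatever the results, and show beside them the number of non-implanted patients and the reasons.

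The cost is a few sentences in the SAP and matching table shells, with no change to data collection. The sponsor gives up a more favourable supplementary success rate.
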